**Improving Walking in Peripheral Artery Disease**  
**ClinicalTrials.gov Identifier (NCT Number): NCT05103280**

## VA Tennis Shoes Protocol

**Title:** Improving Walking in Peripheral Artery Disease, Using Specially Designed Assistive Shoes

**Objective:** The objective of this research is to evaluate the ability of different **specially designed tennis shoes** to improve walking performance, muscle oxygenation of patients with peripheral artery disease (PAD).

**Hypothesis:** We hypothesize that the specially designed tennis shoes will provide assistance to the ischemic legs of patients with PAD and will therefore reduce the biological contribution and oxygen requirements of the ischemic leg muscles. This will acutely increase the walking performance, muscle oxygenation in the patients.

If our hypothesis is correct, the carbon fiber insole shoes and spring shoes may become a new effective conservative intervention for patients with PAD. However, if none of the components of our hypothesis are correct, then our study would direct us away from the carbon fiber insole shoes and/or spring shoes and toward other therapies.

We also hypothesize that an intervention with specially designed tennis shoes (spring loaded or carbon fiber insole shoes) will increase physical activity, and improve walking performance and quality of life. Our preliminary results show promising results in increasing the walking distances including initial claudication distances and absolute claudication distances during first-time use of the specially designed tennis shoes. Subjects will complete a 3month intervention with their preferred specially designed tennis shoe based on the initial data collection. They will be tested prior to starting the intervention and after 3 months of the intervention.

**Endpoints measured:** The patients will walk while wearing their own walking shoes, the carbon fiber insole shoes and the spring-loaded shoes (in random order) and we will measure the following performance endpoints for both phases:

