- 1) **Initial and maximum claudication distance on our instrumented treadmill using the Gardner protocol:** Subjects will complete a Gardner treadmill walking. Subjects will walk in a dynamic gait and pressure analysis treadmill (FDMT Scifit AC500M, Noraxon USA, Inc., Scottsdale Ariz) located at the VA Medical center at Omaha. This treadmill collects synchronized pressure measurements allowing for gait analysis and the calculation of steps taken during exercise. Participants initiated exercise at 2.0 miles per hour at 0.0% incline. With each subsequent 2-minute stage, the treadmill incline was increased 2.0% to a maximum of 12.0%. Time of initial symptoms (claudication onset time [COT] and time at which claudication symptoms were prohibitive to further walking [peak walking time] will be recorded. Data will be collected using regular shoes and specially designed (carbon fiber insole shoes and spring) shoes. They will be allowed to rest for 15 minutes between tests. Patients will do 3 walks in the treadmill (regular walking shoes, carbon fiber insole shoes, and spring shoes).

2) **Calf muscle saturation at one-minute walking:** Bilateral gastrocnemius muscle oxygenation (StO2) will be measured using continuous-wave near infrared spectroscopy (PortaMon, Artinis Medical System, Netherlands) before, during and after each treadmill walking condition (described above). Measurements will be continuously captured during the exercise and recovery interval. We will measure resting StO2 and StO2 at 1-minute walking.

3) **Vertical ground reaction forces in the first two minutes of walking:** Biomechanical data will be collected with a dynamic gait and pressure analysis treadmill (FDMT SciFit AC5000M, Noraxon USA, Inc.). The parameter measured will be the vertical ground reaction force.

4) We will use the Borg Rating of Perceived Exertion (RPE) questionnaire after each condition

5) **Physical Activity:** Participants will wear the Actigraph (Actigraph GT3X, Actigraph, FL, USA) accelerometer on their hip for seven days (the whole day except when sleeping) prior to starting the intervention phase to measure baseline activity level and seven days after the intervention phase to measure post-intervention physical activity. Average steps/day, maximum cadence, and average peak activity index will be calculated.

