#### **2. Patients will perform Gardner protocol on the pressure treadmill at the VA at Omaha, NE.**

- a. Normal walking shoes

- b. Carbon fiber insole shoes
  - c. Spring loaded shoes
- 3. Clinical data to be collected
  - a. ABI
  - b. Medical conditions/comorbidities
- 4. Voluntary Data Repository- If the patient agreed a study and health data will be de-identified and store in a special VA research drive only available to authorized research personnel. Information will be used for future studies about PAD or other vascular diseases. If the patient agrees he will be asked to sign a special HIPPA form.

**Statistical Analysis:** The sample size was calculated to detect effect sizes observed in pilot data for ankle plantarflexor push off. A sample size of 30 subjects will provide 79% power to detect differences of 0.30 standard deviations between walking with control and assistive tennis shoes, using a paired t-test for sample size estimation purposes only, and a significance level of 0.02 to informally adjust for multiple testing. For statistical analysis, a linear (or generalized linear, as appropriate) mixed modeling approach will be used. This approach will allow us to detect differences between walking with and without an AFO while adjusting for confounding variables. The level of significance will be set at 0.05.

Descriptive statistics will be used to summarize results of survey data. We will use counts and percents for categorical data and means and standard deviations for quantitative data. Associations between walking performance and comfort, fatigue, perceived intensity, and feasibility variables will be examined using t-tests for dichotomous variables and correlations for continuous variables. Comparisons will be done independently for each shoe type.

We expect differences from a 3-month intervention to be larger than the immediate differences shown in Aim 1. A sample size of 30 subjects would provide 80% power to detect differences of 0.59 standard deviations between walking with and without assistive tennis shoes, using a paired t-test for sample size estimation purposes only, and a significance level of 0.025 to adjust for multiple testing. For this pilot study, we plan to collect 10 subjects after the intervention and seek additional funding to fully power the study.

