For statistical analysis, a linear mixed modeling approach (or generalized linear mixed model, as appropriate) will be used. This approach will allow us to detect differences within and between groups (different types of assistive shoes), and adjust for confounding variables. The main comparison of interest will be changes in walking distances due to wearing the assistive shoes. This pilot study will allow us to detect if walking distances improve after wearing the assistive shoes for 3-months. To evaluate the relationship between improvements in walking performance, physical activity, and quality of life, multiple correlations will be used. The level of significance will be set at  $p=0.05$ .

Outcome measure	Mean 1	Mean 2	Difference	Standard Deviation	Power	Required Sample Size
Push-off 	1.4	1.7	-0.3	0.30	0.79	29
Visual analog scale 	5.0	7.0	-2.0	2.00	0.81	30
Borg (scenario 2) 	14.0	11.0	3.0	2.50	0.81	23

Assumptions for sample size calculations to obtain 80% power. The test statistic is a two-sided paired t-test with an assumed correlation between mean 1 and mean 2 of 0.30. The alpha level is assumed as 0.001 to account for multiple comparisons between the different shoe types. Mean 1 is assumed as normal walking the control shoe and mean 2 is walking in the best assistive shoe. Choosing the largest sample size across all measures will ensure the desired power for all outcome measures\*.

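### The three-month main comparison covers two walking distances at 0.05 with no lead or split, although the phase was sized at 0.025 for multiple testing

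*Combined protocol and SAP*

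**What the plan says.** The fourth paragraph of Statistical Analysis, on the intervention phase, sets one priority: "The main comparison of interest will be changes in walking distances due to wearing the assistive shoes". It plans a linear or generalized linear mixed model and puts the significance level at 0.05.

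Two variables fit the outcome so described. Endpoints measured, item 1, lists "Initial and maximum claudication distance on our instrumented treadmill using the Gardner protocol" as a single entry, recorded as the time of first symptoms and the time at which symptoms stop the walk. The Hypothesis section uses the same plural term for both when it describes the preliminary results: "increasing the walking distances including initial claudication distances and absolute claudication distances during first-time use". The documents name no lead distance, no testing order, no rule on whether one or both must be significant, and no division of the significance level between the two.

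Multiplicity is mentioned only where sample size is discussed:

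- The baseline-phase sizing (first paragraph of Statistical Analysis) uses "a significance level of 0.02 to informally adjust for multiple testing".
- The intervention-phase sizing (third paragraph) uses "a significance level of 0.025 to adjust for multiple testing".
- The note under the sample size table assumes 0.001 and ties it to comparisons between shoe types.

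The third paragraph also calls this phase a pilot, with 10 patients to be measured after the intervention and further funding to be sought for a fully powered study.

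**The concern.** A comparison declared as the main one should correspond to one test, or to a set of tests with a stated rule. Here a shoe with no effect gets two chances to show an improvement. A report could lead with whichever distance moved and still be following the plan. The stated 0.05 would then not be the error rate of the comparison that the plan puts first.

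The sizing paragraph shows that the authors had some multiple testing in mind for this phase, but it does not say which tests the 0.025 covers. The analysis paragraph that follows uses 0.05. A reader cannot tell which level governs the result. Although it is a pilot, the plan says that this phase will allow improvement in walking distances to be detected, and its result may inform the larger study that the team hopes to fund.

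**Working it through.** **Inputs from the documents.** Two distances (Endpoints measured, item 1); analysis level 0.05 (Statistical Analysis, fourth paragraph); sizing at 30 patients, 0.59 SD, level 0.025 and 80% power, with 10 patients planned (third paragraph). Item 1 records times. It gives a speed of 2.0 mph and raises only the incline, so time and distance carry the same information and the count of two stands.

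**Assumptions.** The correlation between the changes in the two distances is not given, so a range of 0 to 0.9 is used. The 0.30 in the note under the sample size table is the correlation between the two shoe conditions for one measure, and it does not apply here. Either distance alone is taken to count as a positive. A two-sided paired t-test stands in for the mixed model, as it does in the plan's own sizing.

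**Step 1: the plan's own figure.** For a paired t-test the noncentrality is effect × √n = 0.59 × √30 = 3.23, with 29 degrees of freedom. At two-sided 0.025 the power is 80.2%, and 30 is the smallest sample that reaches 80%. The stated figure reproduces, so 0.025 was the level actually used in sizing.

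**Step 2: error rate with two tests at 0.05.** With no effect on either distance and no correlation, the chance of at least one significant result is 1 − (1 − 0.05)² = 1 − 0.9025 = 9.75%. For correlated changes, paired t-tests were simulated with 10 patients (400,000 runs per row). The last column repeats this with each distance tested at 0.025.

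| Correlation of the two changes | At least one positive, 0.05 each | At least one positive, 0.025 each |
|---|---|---|
| 0 (exact) | 9.75% | 4.94% |
| 0.3 | 9.6% | 4.9% |
| 0.5 | 9.1% | 4.6% |
| 0.7 | 8.6% | 4.5% |
| 0.8 | 8.0% | 4.2% |
| 0.9 | 7.2% | 3.75% |

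The exact entry at 0.025 is 1 − 0.975² = 4.94%. Simulations with 30 patients give nearly the same values (for example 9.1% at correlation 0.5 and 7.2% at 0.9, for 0.05 each), so the small sample is not what drives the result.

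**Step 3: what the stricter level costs.** With 10 patients and the plan's 0.59 SD, the noncentrality is 0.59 × √10 = 1.87, with 9 degrees of freedom. Power for one distance is 38.5% at two-sided 0.05 and 26.5% at 0.025.

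**Step 4: if both distances had to be significant.** With no effect on either, the chance that both are positive is 0.05 + 0.05 minus the chance of at least one. That is 10% − 9.75% = 0.25% at correlation 0 and 10% − 7.2% = 2.8% at 0.9. The inflation therefore depends on the either-one reading, which the plan neither states nor rules out.

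**The case against.** The strongest reply is that the plan does allow for multiplicity in this phase. The 0.025 is half of 0.05, it is not tied to shoe types as the 0.001 is, and each patient in this phase wears one preferred shoe. It could therefore be meant for the two distances, and if it were applied to each of them the error would stay below 5%. This stands in part: a reader might infer that the plan ignores multiple testing, and that would be wrong. But the 0.025 could equally be meant for the two shoe types. The paired t-test behind it is said to serve sample size estimation only, and the analysis paragraph sets 0.05. The text does not let a reader conclude that each distance will be tested at 0.025.

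A second reply is that this is a 10-patient pilot with no designated primary endpoint. That limits the harm and is accepted. It does not remove the point, because the plan declares a main comparison and attaches a significance level to it.

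Two stronger readings are not supported. A reader might take a single figure, such as 8% to 9%, as the plan's error rate. That needs an assumed correlation of about 0.5 to 0.8 as well as the either-one rule, and the documents give neither. A reader might also carry the point over to the single-session shoe comparison in the baseline phase, where the level is again 0.05. But the sentence on the main comparison sits within the three-month text, and the first-phase sample size was based on ankle push-off. The documents do not make walking distance the main outcome there.

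**Conclusion.** The point holds for the intervention phase. The main comparison covers two outcomes at 0.05 without a decision rule, and the 0.025 used in sizing is not reconciled with that level. If either distance counts, the false-positive rate for one shoe contrast is about 7% to just under 10%, an excess of roughly 2 to 5 percentage points over the stated 5%. This rests on an assumed correlation between 0 and 0.9, on the either-one reading, and on the paired t-test as a stand-in for the mixed model. The mismatch between 0.025 and 0.05 needs no assumption. The plan should be corrected, but in a pilot of 10 patients the practical consequence is modest.

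**What to change.** In the fourth paragraph of Statistical Analysis, before data are seen, state one of the following for the three-month comparison:

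1. Both distances are main outcomes and each is tested at two-sided 0.025, the plan's own sizing level. The chance of at least one false positive is then about 3.75% to 4.9% over the correlations examined.
2. Both distances are main outcomes and are tested by Holm's procedure at an overall 0.05. The smaller p-value is compared with 0.025 and, if that is significant, the larger with 0.05. This also holds the error at or below 5%.
3. One distance, chosen by the sponsor, is the main outcome at 0.05. The other is secondary and is reported as an estimate with a 95% confidence interval.

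In the same place, say which tests the 0.025 in the sizing paragraph covers, and make the sizing and analysis levels agree. If it was meant for shoe types, the two distances still need one of the rules above.

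The change takes a sentence or two and needs no new patients or data. Option 1 lowers power per distance from about 39% to about 26% with 10 patients at 0.59 SD. Holm recovers part of that loss when the other distance is significant. Under option 3 the secondary distance cannot be claimed on its own. Testing the second distance only after the first is significant is also valid, but it is costly here: with 38.5% power at the gate, the second test would be blocked in 100% − 38.5% = 61.5% of trials even if the lead distance truly improved by 0.59 SD.
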